## Intervention

The intervention will be based on one used previously in Jamaica. It will be modified for Bangladesh following an initial rapid survey of child rearing practices. The mothers will meet in groups at the feeding center for one hour every week for a year. During the initial days, when mothers come daily to the centers, the play leaders will take the opportunity to work individually with mothers and children whenever possible. If the children are judged to be recovered and discharged from the usual services before the end of the year, they will still be included in the stimulation intervention. Those who do not attend will be visited at home and encouraged to come. At the meetings the mothers will be helped to make home made toys and they will be shown how to interact with their children and teach them simple concepts in such a way to improve their development. Only participatory methods or demonstrations will be used. Attention will be paid to improving the maternal child verbal interaction and to improving the mother's self esteem, child rearing and feeding practices. Records will be kept for each child of all contacts with the program staff.

**Training:** A short training workshop will be held to inform and motivate senior staff concerning the program. A two-week workshop will be held for the play leaders who will be running the program

## Facilities Available

Describe the availability of physical facilities at the place where the study will be carried out. For clinical and laboratory-based studies, indicate the provision of hospital and other types of patient's care facilities and adequate laboratory support. Point out the laboratory facilities and major equipments that will be required for the study. For field studies, describe the field area including its size, population, and means of communications. (TYPE WITHIN THE PROVIDED SPACE).

The feeding centers that we will use are organized by CARE and supervised by ICDDR, B. The facilities at the centers will be used for training mothers and observing their children. In addition, we will rent a house in the Narsingdi town where we will conduct the developmental tests. Training of the staff will also be conducted at this house as well as the feeding centers. Data entry and subsequent analysis will be carried out at ICDDR, B offices.

To investigate any illness in the study subjects, we will use ICDDR, B laboratory. Thana health complexes near the feeding centers will be used for referring the ill subjects. In case of severe diarrhea they will be referred to ICDDR, B hospital, while for other serious illnesses requiring tertiary care, Dhaka Shishu Hospital will be contacted.

## Data Analysis

Describe plans for data analysis. Indicate whether data will be analyzed by the investigators themselves or by other professionals. Specify what statistical softwares packages will be used and if the study is blinded, when the code will be opened. For clinical trials, indicate if interim data analysis will be required to monitor further progress of the study. (TYPE WITHIN THE PROVIDED SPACE).

The qualitative data will be analysed using the framework procedures identified by Ritchie and Spencerxxv including indexing, charting, mapping and interpretation.

For the quantitative data, all test records will be checked by a second person and double entered into the computer. All continuous variables will be examined for normality and transformed if necessary. Initial differences between the randomized malnourished groups will be examined using t-tests or analysis of variance for normally distributed data and chi-squared or Mann-Whitney for non-normal data. To compare initial differences between the adequately nourished and malnourished groups the enrolment data for the two malnourished groups will first be combined. When analyzing behavioral data, age and sex will be controlled if they are significantly related to the outcome variable.

As the sample is clustered into feeding centers, multi-level modelling will be used to examine the treatment effect on the children's development, behavior, and temperament and on the maternal outcomes. For this analysis, we will use the computer package designed by the Institute of Education, Londonxxvi. The model used will have 3 levels, the individual child, the feeding centers and the treatment group. With this model we will be able to control for random variance at each of these levels and to examine whether treatment has different effects in different centers.

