### Study Design

A rapid survey comprising holding focus group discussions with women in the villages and interviewing key informants will precede the main study. The main study will be a randomized controlled trial of the effect of adding stimulation to the treatment of malnourished children in feeding centers. Narsingdi thana which is close to Dhaka was recently visited by the investigators and was selected for the study. There are on average 8-10 moderately and severely malnourished children in each feeding center at any time. Twenty selected centers will be randomly assigned to treatment or control groups. (It is not considered ethical to randomize individually within each center). The intervention will run for one year and the outcome measures will be assessed in mothers and children both before and after the study

In addition to the treatment trial, a cohort of matched adequately nourished children will be studied to compare with the malnourished groups. They will come from the same villages served by the intervened centers and will fulfil the same criteria for age, area of residence, and socio-economic background to the intervened children. This comparison will enable us to determine the initial behavioral and psychomotor deficits in the malnourished groups and assess whether the children return to levels normal for their community following intervention.

Recognizing that the children are clustered into feeding centers or villages we will use multilevel modelling in the analyses to enable us to analyze data at the individual child level as well as examine the variance by feeding center and treatment group.

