## Treatment Trial

### Samples

The study will be conducted in BINP nutrition centers in the Narsingdi Thana. Narsingdi which is situated near Dhaka and has a total population of 353,275 out of whom, there are 21,090 children below the age of 2 years. About 2229 of these children require nutritional supplementation and are enrolled in the BINP community nutrition centers. Narsingdi thana comprises 14 unions with 17-29 feeding centers in each union making a total of 326 feeding centers. Only six of these unions are accessible to Dhaka. For ethical reasons randomization into intervention and control will be by centers and not within each center. Twenty feeding centers from the two unions most accessible to Dhaka, will be selected to participate in the study. Only centers expected to enrol at least 10 children in the five month enrolment period will be selected. The sampling will be in two steps. In the first step, centers that are so close to each other that there is a high probability of the mothers or staff mixing socially, will be formed into clusters. One center from each cluster will then be randomly selected for further sampling. The first stage should prevent any spill over between treatment groups. In the second step 10 centers will be randomly selected for the intervention group and 10 for the control group, from the two unions.

A sample of 84 in each group will be sufficient to detect a difference of 6 developmental quotient (DQ) points between the groups with a power of 90% at the 5% level of significance. Assuming a loss of 16% we need 100 children in each group.

The study will have 3 groups making a total of 300 children who will have all measurements. However, because we want to assess the feasibility of incorporating this programme into a service model we will enrol into the intervention all children who present at the centers and fit the enrolment criteria during the enrolment period. The extra children will not have the measurements but enrolling all available children into the intervention will enable us to determine any problem with implementation at a service level.

**Treatment group:** The first 10 children referred to each intervention feeding center after the beginning of the study, and fulfil the selection criteria will be enrolled making a total of 100. However, all the children attending the intervention centers will have play opportunities.

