**Control group:** The first 10 children referred to each control feeding center after the beginning of the study and fulfil the selection criteria will be enrolled making a total of 100.

**Inclusion criteria:** weights for age  $<-2sd$ , aged between 6 and 24 months, mothers agree to participate in the study and intend to stay in the area for the next year.

**Exclusion criteria:** twins and disabled children will be included in the intervention for ethical and demonstration purposes but will not be part of the evaluated sample.

**Comparison group:** The child living nearest to every treated malnourished child with weight for age  $>-1sd$ , of the same age ( $\pm$  one month) and sex, maternal education and standard of housing will be enrolled making a total of 100.

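### Baseline differences between the two randomised malnourished groups are tested with independent-observation tests although 20 centers, not children, are randomised, so the nominal 5% level is exceeded for any positive within-center correlation

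*Protocol*

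**What the plan says.** All references are to the psychosocial stimulation trial, not to the second proposal bound into the same file.

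- **Unit of randomisation.** Study Design: "Twenty selected centers will be randomly assigned to treatment or control groups". Samples: "In the second step 10 centers will be randomly selected for the intervention group and 10 for the control group".
- **Children per center.** Samples, treatment group: "The first 10 children referred to each intervention feeding center after the beginning of the study"; control group: "The first 10 children referred to each control feeding center after the beginning of the study". That gives 100 measured children per arm.
- **Baseline comparison.** Data Analysis: "Initial differences between the randomized malnourished groups will be examined using t-tests or analysis of variance for normally distributed data", with chi-squared or Mann-Whitney tests for non-normal data. No allowance for center is mentioned.
- **Treatment effect.** The next paragraph of Data Analysis gives clustering by center as the reason for a multilevel model, but applies that model to the treatment effect on the child and maternal outcomes.
- **General statement.** Study Design: "Recognizing that the children are clustered into feeding centers or villages we will use multilevel modelling in the analyses". The baseline comparison is not named there.

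Neither an ICC nor a design effect appears anywhere in the protocol.

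**The concern.** Children who attend one feeding center come from the same neighbourhood. Housing, wealth, maternal education, home stimulation and test scores may therefore be more alike within a center than between centers. A t-test or chi-squared test on children ignores this. It takes ordinary variation between centers for evidence that the arms differ, because its standard error counts 100 independent children per arm when only 10 centers per arm were allocated.

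This is the only check of starting comparability that the Data Analysis section states. If it runs above its nominal level, the report may list initial differences that are no more than center-to-center variation and so cast doubt on a sound allocation. The check also has a real purpose here. Children are enrolled after their center has been allocated, so differential recruitment is possible, and a miscalibrated test is poor at separating that from chance.

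**Working it through.** **The plan's own figure.** The only sample-size statement is: "A sample of 84 in each group will be sufficient to detect a difference of 6 developmental quotient (DQ) points between the groups". The stated power is 90% and the stated level 5%. No standard deviation is given. Solving for it, with a two-sided 5% level assumed:

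SD = 6 / [(1.960 + 1.282) × √(2/84)] = 12.0

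At an SD of 12 the power with 84 per group is 0.900, and 84 / (1 − 0.16) = 100 per group. The stated size is reproduced under individual-level assumptions. It contains nothing about clustering that could be carried over to the baseline tests.

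**Inputs for the check.** There are 10 centers per arm and m = 10 children per center at baseline (Samples). Losses come later and do not matter here. The ICC is assumed, over a range of 0.01 to 0.20.

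**Formula.** The true variance of the difference in means exceeds the one the child-level test uses by about DEFF = 1 + (m − 1) × ICC = 1 + 9 × ICC. When the arms differ only by center-to-center variation, the real error rate of the nominal 5% test is about 2 × [1 − Φ(1.96 / √DEFF)].

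Example at ICC 0.05: DEFF = 1.45, √1.45 = 1.204, 1.96 / 1.204 = 1.628, error rate 10.4%.

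| Assumed ICC | DEFF | Formula | Simulated child-level t-test |
|---|---|---|---|
| 0.01 | 1.09 | 6.1% | 6.1% |
| 0.02 | 1.18 | 7.1% | 7.1% |
| 0.05 | 1.45 | 10.4% | 10.3% |
| 0.10 | 1.90 | 15.5% | 15.3% |
| 0.15 | 2.35 | 20.1% | 19.8% |
| 0.20 | 2.80 | 24.2% | 24.2% |

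The simulation used 2 arms × 10 centers × 10 children and 40,000 runs per ICC.

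**The other named tests.** Mann-Whitney behaves like the t-test: 10.1% at ICC 0.05 and 15.6% at 0.10 (3,000 runs). Chi-squared on a trait with 50% prevalence, made by cutting the same variable at its middle, is lower: 9.1% at 0.05 and 12.7% at 0.10.

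**The remedy.** A t-test on the 20 center means (20 − 2 = 18 degrees of freedom) had a simulated error rate of 4.8% to 5.0% over ICC 0 to 0.20. The multilevel alternative was not simulated.

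**The case against.** **The general statement might cover baseline.** Study Design promises multilevel modelling for the analyses because children are clustered, and the section cited never says that the baseline tests are run on children. So the investigators knew of the clustering and planned software for it. That much stands. But Data Analysis is the specific section, and it names other tests for baseline. A t-test or Mann-Whitney test is not a multilevel model, center-level summaries are mentioned nowhere, and Study Design speaks of analysing data on individual children. If the general statement was meant to govern, the two sections need reconciling anyway.

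**The size is not known.** This stands. A reader might infer that false differences appear two to three times as often as 5%. The documents do not support that as a fact. For a t-test, an error rate of 10% to 15% needs an ICC of about 0.047 to 0.095, since ICC = [(1.96/z)² − 1]/9 with z = 1.645 and 1.440. Below that range the inflation is smaller, above it larger, and for chi-squared it is lower at the same ICC. Nor can one count the expected false differences in the baseline table, because the number of baseline variables to be tested is not stated.

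**The harm is limited.** This also stands. A reader might infer that the faulty tests feed into covariate choice or the main result. They do not. The one covariate rule in Data Analysis adjusts behavioral data for age and sex when these are related to the outcome, not when they are unbalanced at baseline. The treatment effect has its own multilevel analysis.

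**Baseline examination is legitimate.** A reader might conclude that baseline tests should simply be removed. That is partly preference. With enrolment after center allocation, a valid test has a use; the clustering defect only requires that it allow for center.

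**Conclusion.** The point holds in a limited form. As written, the baseline comparison of the randomised arms uses tests that do not match the unit of randomisation. This is a stated method, not a detail left for a later plan. The direction is certain for any ICC above zero. The size rests on an assumed ICC: with 10 centers per arm and 10 children each, about 6% at 0.01, 10% at 0.05, 15% at 0.10 and 24% at 0.20 for the t-test, and about 9% at 0.05 and 13% at 0.10 for chi-squared. What is affected is the check of baseline comparability and how it will be reported. The trial's test of the treatment effect is not affected by this point.

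**What to change.** In Data Analysis, replace the sentence on initial differences between the randomised groups by one saying that any test of these differences allows for center. Two forms would do: a multilevel model with children within centers and arm as a fixed term, fitted in the package already planned, or a t-test on the 20 center means (center proportions for binary items) with 18 degrees of freedom. If no test is wanted, say that the arms will be described by means and proportions.

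The cost is one sentence. Sample size, data collection and conduct do not change. Baseline p-values will be larger: by the formula above, a child-level p of 0.05 corresponds to about 0.10 at an ICC of 0.05.

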Recently, there has been increasing concern among international agencies and national governments over the loss of human potential in children growing up with poverty and malnutrition and possible ways of improving the situation are being explored. Bangladesh Integrated Nutrition Program (BINP) is a major governmental effort to improve malnourished children's nutritional status. This program should reduce mortality and morbidity in children but it is unlikely to also improve their general cognitive, social and emotional development. This proposal concerns incorporating a low cost, feasible, and culturally appropriate program of child development activities into BINP feeding centers with the aim of improving the social and cognitive development of malnourished children and the child rearing skills of their mothers. It is a randomized controlled trial involving the BINP feeding centers, where a group of malnourished children and their mothers will participate in an intervention on child development activities and will be compared with a control group of malnourished children attending other feeding centers. They will also be compared with a group of wellnourished children living in the intervention areas and matched for age, sex, maternal education, and standard of housing. Intervention will include teaching mothers how to play with their children in a way to promote good development, and how to make toys from waste materials. Attention will also be paid to improving maternal child verbal interaction and to improving mothers' self esteem. The intervention program will last for one year. Stimulation at home and the socio-economic status of the family will be measured during a home visit. Before and after the study, the children's developmental levels, behavior, temperament and anthropometry and the mothers' knowledge of child development and child rearing practices will be assessed.

KEY PERSONNEL (List names of all investigators including PI and their respective specialties)

Name	Professional Discipline/ Specialty	Role in the Project
1. [name] [name]	SMO./Paediatrics	Principal Investigator
2. [name] [name]	Associate Professor/Nutrition	Co-PI
3. [name]	Associate Scientist/Nutrition	Co-Investigator
4. [name]	Interim Director/Gastroenterology	Co-Investigator
5. [name]	Professor/Child Development	Co-Investigator

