## Measurements

The Drs [name] and [name] will do the piloting and quality control of all measurements.

**Developmental level:** The infants will be assessed on the Bayley Scales of Mental Development at the beginning and end of the study. We have used these scales before in Bangladesh and good interobserver reliability was attained. The assessments will be done by one of two trained female psychologists who are unaware of the children's group assignment. Care will be taken to keep the testers blind to the child's group and the testing will not be done in the feeding centers.

**Behavior:** The children's behavior during the tests will be rated by the testers on five 9 point scales: the amount of vocalisation, co-operation with the test procedure, activity level, emotional tone and response to examiner. These scales have also been used before in Bangladesh and are modified from those of Bayley and Wolke et alxxi.

**Temperament:** At the end of the study the mothers will be given a questionnaire by the psychologists concerning their child's temperament. There is no standardised test for Bangladeshi children. We will therefore pilot an instrument developed by Mary Rothbartxxii and one being developed by Theodore Wachs from Purdue University for use in Jamaica and Peru and combine and modify the instruments where necessary. The following behaviors will be investigated: activity level, positive emotionality (smiling/laughing), negative emotionality (fussing/crying), social approach (response to strange adults), object fear (fear of new objects), attention/orientation, manageability (response to frustration/ co-operativeness), soothability (reduction of distress in response to soothing). These behaviors are well recognised components of temperamentxxiii.

**Anthropometry:** All children will have their weights, lengths, head and mid upper arm circumferences measured using standard techniques on enrolment and every 3 months by the research assistant.

**Socio-economic background and stimulation in the home:** All homes will be visited at the beginning of the study and information will be sought on the families' wealth, standard of housing, family structure and parental characteristics. The stimulation in the home will be assessed using a modified version of the Betty Caldwell home inventoryxxiv, which was modified for Bangladesh in a previous study by this research group.

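### The Data Analysis section does not say how baseline Bayley, behavior and maternal scores enter the treatment-effect model, its only covariate rule depends on the outcome data, and the temperament schedule contradicts itself.

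*Protocol*

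**What the plan says.** All references are to the psychosocial stimulation protocol.

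- **Treatment model (Data Analysis).** The protocol states that "multi-level modelling will be used to examine the treatment effect on the children's development, behavior, and temperament and on the maternal outcomes". The model is then described by three levels: child, feeding center and treatment group. No fixed covariate is listed. The section does not say whether the outcome is the end score or the change from baseline.
- **Use of enrolment data (Data Analysis).** Two uses are stated: significance tests of initial differences between the randomized groups, and a comparison of the combined malnourished groups with the adequately nourished children.
- **Covariate rule (Data Analysis).** For behavioral data, "age and sex will be controlled if they are significantly related to the outcome variable".
- **What is measured twice (Measurements).** "The infants will be assessed on the Bayley Scales of Mental Development at the beginning and end of the study". Behavior is rated during those same tests. Mothers' knowledge and child-rearing practices are also assessed at both times.
- **Temperament.** Measurements says "At the end of the study the mothers will be given a questionnaire by the psychologists". The Project Summary lists "developmental levels, behavior, temperament and anthropometry" among the things assessed before and after the study, and the abstract for the Ethical Review Committee repeats this. Study Design says of the outcome measures in general that they are assessed both before and after.
- **Sample size (Samples).** The section states that "A sample of 84 in each group will be sufficient to detect a difference of 6 developmental quotient (DQ) points between the groups". The stated power is 90% and the significance level 5%. An allowance of 16% for loss brings the enrolment target to 100 per group.

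**The concern.** The trial pays for a full baseline assessment and then describes the treatment-effect model without giving that assessment a place in it. With 10 centers per arm, the arms can differ by chance in starting development. Conditioning on the baseline score removes the part of that difference which carries through to the end score, and it reduces the residual variance. Leaving the choice open also leaves room to adjust or not after the tests of initial differences have been seen.

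The stated rule for age and sex has a similar weakness. Whether they are included depends on a significance test against the trial's own outcome. Children are enrolled from 6 to 24 months, and the ratings cover vocalizing, activity and co-operation, which may well vary with age.

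The temperament conflict is a different kind of problem. It concerns consistency and what can be estimated, not precision. An analysis plan cannot recover a baseline that was never collected.

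**Working it through.** **1. Reproduce the stated sample size.** The inputs from Samples are 6 DQ points, 90% power, 5% significance (two-sided assumed), 84 per group and 16% loss. The SD is not given, so it is solved for:

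SD = 6 × √(84/2) / (1.960 + 1.282) = 12.0.

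A one-sided test would imply 13.3. Loss: 84 / (1 − 0.16) = 100, as stated. The 84 therefore fits an unadjusted, individually randomized comparison with SD about 12.

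**2. Power with 10 centers per arm.** The inputs are SD 12 (back-solved), 84/10 = 8.4 evaluable children per center, and a t test on 18 df (20 centers − 2). The ICC and r (baseline-to-end correlation) are assumptions.

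Variance of the treatment difference:

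V = 2 × 12² × [ (1 − ICC)(1 − r²)/84 + ICC(1 − r_c²)/10 ]

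Here r_c = r if the baseline explains center-level variance equally well, and r_c = 0 if it explains only child-level variance.

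Example, ICC 0.05, unadjusted: V = 288 × (0.95/84 + 0.05/10) = 4.70, SE 2.17, power 74%.
With r = r_c = 0.5: V = 4.70 × 0.75 = 3.52, SE 1.88, power 86%.
With r = 0.5, r_c = 0: V = 288 × (0.95 × 0.75/84 + 0.05/10) = 3.88, SE 1.97, power 82%.

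Power for 6 DQ points (lower figure: child-level only; upper: both levels):

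| r | ICC 0.05 | ICC 0.10 |
|---|---|---|
| unadjusted | 74% | 64% |
| 0.3 | 77–78% | 66–68% |
| 0.5 | 82–86% | 70–77% |
| 0.6 | 86–91% | 73–83% |

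**3. Likely size of a chance baseline difference.** With 100 per arm and the same SD, the SE of the baseline difference is √{288 × [(1 − ICC)/100 + ICC/10]}. That is 2.0 points at ICC 0.05 and 2.3 at ICC 0.10, against a target of 6.

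**4. Temperament, side by side.** Measurements: end only. Project Summary and Ethical Review Committee abstract: before and after, with temperament named. Study Design: before and after for outcome measures generally. The first cannot hold together with the other three.

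**The case against.** The strongest reply is that silence is not a decision. A reader might infer that the trial will not adjust for baseline. The documents do not say so: Data Analysis describes the levels of the model and leaves its fixed part unstated. Covariate lists are commonly left to a statistical analysis plan, and none is shown. This stands, so the point is limited to what the protocol leaves undefined and what it fixes badly.

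Three further objections have force.

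- **Bias.** A reader might infer that chance imbalance invalidates the result. It does not. Under randomization the unadjusted estimate is unbiased and its standard error already reflects such imbalance. The argument is about efficiency.
- **Scope of the age and sex rule.** The sentence closes the paragraph on initial differences, before the treatment model is introduced, so it may not govern that model. The protocol does not settle this. In addition, the Background says that socio-economic background and home stimulation will be related to the effects of malnutrition and of treatment, so age and sex are not the only baseline variables with a planned role.
- **Objective 3.** A reader might infer that it demands an enrolment deficit in temperament. It names no time point, and Study Design describes the initial deficits only as behavioral and psychomotor. An end-of-study temperament comparison could still serve the objective.

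The size of the gain is also uncertain. It is only about 2 to 4 points of power at r = 0.3, and at ICC 0.10 about half or more of the gain at r = 0.5 or 0.6 disappears if the baseline explains only child-level variance.

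None of this removes the two faults in the text: the significance-dependent covariate rule and the temperament conflict.

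**Conclusion.** The concern holds as a matter of specification and precision. Data Analysis does not define how the collected baseline scores enter the treatment-effect model, and the one covariate rule it does state depends on the outcome data. The direction of the benefit is clear. Its size rests on assumptions about SD, ICC and r, none of which the protocol supplies. At SD 12 and r = 0.5, adjustment adds roughly 8 to 11 points of power at ICC 0.05 and 6 to 12 at ICC 0.10. The documents support neither the claim that baseline has been excluded nor the claim that the unadjusted estimate would be biased.

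The temperament conflict is certain and needs no assumptions. If the questionnaire is given only at the end, temperament has no baseline to adjust for and no enrolment comparison between malnourished and adequately nourished children.

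**What to change.** 1. State in Data Analysis that each end-of-study outcome measured at both times is modelled on treatment plus the same child's or mother's baseline score, age and sex. These terms are always included, whatever the tests of initial differences show, with a random intercept for center.
2. Delete the rule that includes age and sex only when they are significantly related to the outcome.
3. Reconcile the timing of the temperament questionnaire across Measurements, Study Design, the Project Summary and the Ethical Review Committee abstract. If it stays end-only, say that temperament is analyzed without a baseline score and has no enrolment comparison.

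Items 1 and 2 cost only analysis wording. For item 3, an end-only schedule costs nothing in the field. Keeping a baseline adds time to the psychologists' existing interview with the mothers. That time is not trivial, since the questionnaire covers eight temperament domains and 300 mothers are to be interviewed.
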